2.0 Objectives

The objective of this study is to determine if VR goggles can decrease patient pain and anxiety during simple laceration repairs. The primary outcome will be pain scores as assessed by the validated Wong Baker Faces Scale and anxiety scores as assessed by the validated Children's Fear Scale. A validated System Usability Scale (SUS) will be measured for each enrolled participant that used the VR goggles. Secondary outcomes include time of procedure, use of physical holding, adverse outcomes, and pharmacologic interventions.

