3.0 Project Procedures

This will be a randomized pragmatic study for all patients ages 6-17 years with simple lacerations. Simple lacerations will be defined as lacerations within the scope of pediatric emergency medicine providers AND not requiring sedation or operative intervention. Subjects will be identified by the Emergency Department staff for enrollment. The goal number of enrolled participants will be 480, including 240 patients randomized into two groups, 120 per group, and 240 parents/guardians. The Emergency Department accepted to participate in this study and ED providers will complete the provider's survey. After signing the consent and assent form when appropriate, the patients will be randomized to either receive the standard of care or standard of care with immersive virtual reality goggles. Consent and assent will be obtained in the patient rooms within the emergency department. The standard of care shall be defined to include any of the following: local analgesia (topical LET and/ or subcutaneous lidocaine), oral or intranasal midazolam, distraction, Child Life Staff, or physical holding. Because each of the aforementioned interventions may vary between patients, it cannot be truly standardized; hence, this will be considered a pragmatic study. Patients randomized to the VR arm will receive the other standard procedures as well with VR goggles as an adjunct. Exclusion criteria include a history of epilepsy, visual or hearing impairment, or intellectual disability that would preclude use of VR goggles as determined by the guardian. Additionally, any lacerations around the eyes, eyebrows, and nose will be excluded as well as patients requiring sedation. Non-English speaking patients will be excluded as well. Hand lacerations will not be excluded.

Participants will be identified by ED staff following evaluation of the laceration. The ED staff will be given a flowchart with eligibility criteria. All interested participants who meet eligibility criteria will be consented. A research team member will obtain consent from parents or guardians by providing and reviewing the consent form (see Subject Consent Form). For patients who are between 8 and 17 years of age, a research team member will obtain assent by providing and reviewing the assent form (see Subject Assent Form). Consent and assent will be obtained in the patient's ED room.

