5.0 Risks to Participants/ HIPAA Privacy Considerations

No personal identifiers will be recorded as part of the research study. Each enrolled participant will be given a unique number for data collection purposes. The risks involved in the study include adverse reactions to the VR goggles, which have been described to rarely cause nausea, vomiting, and motion sickness. There is a theoretical infection risk, but the VR goggles will be cleaned following a decontamination protocol following each use.

The data will be securely stored in RedCAP without any patient identifiers. The paper surveys will be kept in a locked drawer in a locked room within the Pediatric Department of Emergency Medicine offices.

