6.0 Budget

The Virtual Reality goggles are property of the Children's Hospital of the King's Daughters Child Life department. They will be stored in a locked drawer within the CHKD Emergency Department. This project is unfunded.

Figure 1. Use of Immersive Virtual Reality for Laceration Repairs in the Pediatric Emergency
Department
Patient Survey

1. How old are you? _____

2. Have you had stitches before? Yes
 No
 Unsure

3. Have you ever used Virtual Reality (VR) goggles before today? Yes
 No
 Unsure

4. Did you use VR goggles for your stitches today? Yes
 No

5. Would you use VR goggles again to get stitches? Yes
 No

6. During your stitches, did you have any of the following (select all that apply)?
 I did not experience any symptoms
 Dizziness
 Headache
 Nausea
 Vomiting
 Other (describe below)

7. How do you think the stitches went overall? Not well at all
 Somewhat not well
 Neutral
 Somewhat well
 Very well

8. The virtual reality goggles made the stitches seem less scary.
 Strongly disagree
 Disagree
 Neutral
 Agree
 Strongly agree

9. How would you rate your pain:

10. How would you rate how scared you were during the stitches:

[figure not shown]

Figure 2. Use of Immersive Virtual Reality for Laceration Repairs in the Pediatric Emergency
Department
Guardian Survey

1. **Patient Gender:**

Male
 Female
 Non-binary
 Self-identify
 Prefer not to say

2. What is the patient's age? _____

3. Please indicate if the patient has a developmental disability:

A. The patient does not have a developmental disability
B. Autism
C. Cerebral Palsy
D. Intellectual disability
E. Speech delay
F. _____

4. Has the patient had stitches previously? _____

Yes
 No
 Unsure

5. Has the patient ever used Virtual Reality (VR) goggles before today? _____

Yes
 No
 Unsure

6. Did the patient use VR goggles for the procedure today? _____

Yes
 No

7. If, yes, would you use VR goggles again for this procedure? _____

Yes
 No
 Did not use today

8. During the procedure did the patient experience any symptoms (select all that apply)?

Did not experience any symptoms
 Dizziness
 Headache
 Nausea
 Vomiting
 Other (*describe below*)

9. How do you think the procedure went overall?

- Not well at all
- Somewhat not well
- Neutral
- Somewhat well
- Very well

10. In your opinion, did the virtual reality goggles make the procedure seem less scary to the patient?

[figure not shown]
- Strongly disagree
- Disagree
- Neutral
- Agree
- Strongly agree

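### No symptom check or wound site is recorded before the envelope, so a reported symptom cannot be attributed to VR in an individual child and the between-arm comparison, though unbiased by injury symptoms, loses precision

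*Combined protocol and SAP*

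**What the plan says.** **Role of the outcome.** Section 2.0: "Secondary outcomes include time of procedure, use of physical holding, adverse outcomes, and pharmacologic interventions". Section 5.0 gives the expected reactions to the goggles, "which have been described to rarely cause nausea, vomiting, and motion sickness".

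**Who can enter.** Section 3.0 defines a simple laceration by provider scope and treatment need, not by body site: "lacerations within the scope of pediatric emergency medicine providers AND not requiring sedation or operative intervention". The only site exclusion is "any lacerations around the eyes, eyebrows, and nose will be excluded as well as patients requiring sedation". The medical exclusions are "a history of epilepsy, visual or hearing impairment, or intellectual disability that would preclude use of VR goggles as determined by the guardian". Head injury and symptoms on arrival do not appear in either list.

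**What happens before allocation.** "Participants will be identified by ED staff following evaluation of the laceration". Staff use an eligibility flowchart, consent is taken, and a sealed envelope is chosen. No symptom record is described at any of these steps.

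**How symptoms are measured.** They are asked once, after the repair. The patient form (Figure 1, item 6) reads "During your stitches, did you have any of the following (select all that apply". Figure 2 item 8 and Figure 3 item 6 put the same four symptoms to the guardian and the provider. All three items refer to the repair period, none depends on having used VR, and none asks whether the symptom was new or worse. No form has a field for wound site or mechanism of injury.

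**Analysis.** Section 4.0 plans a generalized linear model for the effect of the intervention on the survey outcomes, two-sided at 0.05, with no covariates named.

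**The concern.** The four listed symptoms can follow a blow to the head as well as a VR headset. A child with a scalp or forehead wound outside the excluded areas who arrives with a headache or nausea is eligible, may be allocated to VR, and would answer item 6 truthfully by ticking a symptom that began before the goggles went on. The form gives no means of separating that tick from a new symptom.

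The expected VR effect is described as rare, so even a small injury background could be as large as the effect itself. Counts from the VR arm could then mislead anyone reading them as side effects, and a real excess over control would be harder to see. The gap cannot be closed later from the planned data: the forms hold neither arrival symptoms nor wound site, and Section 5.0 has the data stored without identifiers and describes no link back to the chart.

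**Working it through.** **Inputs from the documents.** 240 children, 120 per group (Section 3.0); two-sided 0.05 (Section 4.0). The headcount adds up: 2 × 120 = 240, and 240 + 240 guardians = 480. No power, effect size or event rate is stated, so there is no design calculation to reproduce.

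**Assumptions, since the documents give no rates.**
- Injury background *b* = (share with a head wound) × (share of those with a listed symptom). With 10–30% and 10–20%: 0.10 × 0.10 = 1% up to 0.30 × 0.20 = 6%, or 1.2 to 7.2 of 120 children per arm.
- Symptoms from any other cause: 1%.
- VR-caused risk *v* of 2–5%: 2.4 to 6.0 of 120 children. 10% is used as a high case.
- Injury symptoms are present before the envelope, so a check would find them.

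**Formulas.** Control rate pc = 0.01 + 0.99*b*. VR-arm rate pv = pc + (1 − pc)*v*. Share of symptomatic VR-arm children whose symptom is due to VR = (pv − pc)/pv. Power = Φ[(|pv − pc| − 1.96·se0)/se1], with se0 the pooled and se1 the unpooled standard error. With a check, only children symptom-free beforehand are analysed: about 120(1 − *b*) per arm, with rates 0.01 and 0.01 + 0.99*v*.

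**One line in full (b = 6%, v = 5%).** pc = 0.01 + 0.99 × 0.06 = 0.0694. pv = 0.0694 + 0.9306 × 0.05 = 0.1159. Difference 0.0465; share due to VR 0.0465/0.1159 = 40%. se0 = √(0.0927 × 0.9073 × 2/120) = 0.0374; se1 = 0.0373. Power = Φ[(0.0465 − 1.96 × 0.0374)/0.0373] = Φ(−0.72) = 0.24. With the check, 112 per arm, 0.0100 against 0.0595: power 0.53.

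**Results for v = 5%.**

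| b | Control rate | VR-arm rate | Difference | Share due to VR | Power as planned | Power with check (n per arm) |
|---|---|---|---|---|---|---|
| 0% | 1.0% | 6.0% | 5.0 points | 83% | 0.55 | 0.55 (120) |
| 1% | 2.0% | 6.9% | 4.9 points | 71% | 0.45 | 0.55 (118) |
| 3% | 4.0% | 8.8% | 4.8 points | 55% | 0.33 | 0.54 (116) |
| 6% | 6.9% | 11.6% | 4.7 points | 40% | 0.24 | 0.53 (112) |

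For v = 10% and b = 6%, power is 0.62 as planned and 0.89 with the check. For v = 2%, power is 0.19 even at b = 0. With so few events the normal approximation is rough, so the last two columns should be read against each other, not as exact values.

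**Is the arm difference biased?** In 200,000 simulated trials with v = 5%, the mean difference was 0.0480 (true 0.0480) at a 4% background and 0.0439 (true 0.0440) at 12%. There is no bias. The true difference shrinks a little as background rises, because a child who already has a symptom cannot be counted again.

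**Precision.** The smallest excess detectable with 80% power at 120 per arm grows from 7.8 points at a control rate of 1% to 10.5 at 4% and 11.7 at 6%. With a 4% background in both arms, the chance imbalance is about ±1.96 × √(2 × 0.04 × 0.96/120) = ±5.0 points (95%).

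**The case against.** A reader might infer that VR side effects cannot be told from injury symptoms at all, or that the plan overstates the VR rate. The documents do not support either reading. Section 3.0 provides a concurrent randomized control arm, the symptom item goes to both arms whether or not VR was used, and Section 4.0 plans a comparison between arms. Injury symptoms are balanced in expectation. Nowhere does the plan say that VR-arm counts will be read alone or that staff will attribute individual cases.

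Three further objections have force.
- Every rate above is assumed. Within the same ranges, low background against high signal is 1.2 against 6.0 children, so the background need not rival the VR effect.
- The pooled count of any listed symptom is a construct of this check. Section 5.0 does not name headache as a VR risk, and the tick list allows analysis by symptom.
- For rare effects the sample size is the main limit: at v = 5% power is only 0.55 with no injury background.

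It is also fair that the plan names no scalp or forehead wounds and that the eligibility flowchart is not reproduced. The accurate statement is that no screen is described, not that none exists.

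What survives is the loss of attribution in individual children and the loss of precision. Randomization also does not equalize reporting. Respondents know the allocation, and each form asks about goggles use before it asks about symptoms, so an existing headache may be ticked more readily after VR. A record made before allocation reduces that problem without removing it.

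**Conclusion.** The point holds as a minor, inexpensive improvement to a secondary safety outcome. As planned, a listed symptom cannot be attributed to VR in an individual child, and the raw VR-arm rate mixes VR effects with injury symptoms. The between-arm difference is not biased by injury symptoms; it is less precise.

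The size depends on rates the documents do not give. With 1% other background and v = 5%, an injury background of 1–6% takes power from 0.55 down to 0.45–0.24, and a pre-envelope check brings it back to 0.55–0.53. If few children with head wounds enrol, the loss is small. The check does not make the trial adequate for rare reactions. It removes an avoidable part of the noise and makes single cases interpretable.

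**What to change.** 1. **Before the envelope is opened**, have research staff record for every child the same four symptoms (present or absent) and wound site or head injury (yes or no).
2. **Define the adverse outcome** as a listed symptom reported during the repair that was absent, or milder, on the pre-envelope record. A yes/no record settles absent but not milder. If worsening is to count, add a simple severity grade or report worsening separately as a respondent's judgement.
3. **Use the same observation window in both arms**, for example from allocation to wound dressing, and word the item on all three forms to match. Arm-specific starts, such as headset on for VR and irrigation for control, would observe the arms over different periods.
4. **Report by symptom**, as a between-arm difference with a confidence interval, and do not present VR-arm counts alone as side effects.

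Whether children with such symptoms are eligible for goggles is for the sponsor's clinicians to state; no rule is proposed here.

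**Cost.** Under a minute per child, by staff already present for consent, and one reworded item on each form. The reported count will be slightly lower, and some bias from unblinded reporting remains in any judgement that a symptom got worse.

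### On all three survey forms the pain and fear ratings come last, directly after an item asking whether VR made the procedure less scary; placing them first removes an avoidable order effect

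*Combined protocol and SAP*

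**What the plan says.** Section 2.0 names pain (Wong-Baker faces) and anxiety (Children's Fear Scale) as the primary outcome. It does not say whose rating counts. Section 3.0 collects both scales on paper after the repair, from patient, guardian and provider, using the forms in Figures 1 to 3.

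On the patient form (Figure 1), item 4 is "Did you use VR goggles for your stitches today", item 5 is "Would you use VR goggles again to get stitches" and item 7 is "How do you think the stitches went overall". Then come "8. The virtual reality goggles made the stitches seem less scary", "9. How would you rate your pain" and, last, "10. How would you rate how scared you were during the stitches". The guardian and provider forms (Figures 2 and 3) end in the same way: overall impression, the less-scary question, pain, fear.

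The only ordering rule in the text is in Section 3.0: the parent fills in the guardian form before the child's form, in case the child needs help. Nothing covers item order within a form, and no reason is given for the printed order. Section 4.0 plans a GLM for the effect of the intervention on the survey outcomes.

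**The concern.** Patient item 8 and patient item 10 are about the same thing. A child is asked to judge whether the goggles reduced fear and, one item later, is asked how frightened he or she was. An answer just given can pull the next one into line with it.

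An order effect that is equal in both arms cancels from the comparison. Here there is reason to think it may not be equal. A child in the VR arm judges goggles actually worn. A standard-care child meets the same statement about goggles not worn, and patient items 5 and 8 offer no way to say so. The effect could favour VR (the child has just agreed that it helped) or count against it (the child has just recorded disappointment).

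At stake is the between-arm contrast in the ratings that carry the primary outcome. If the child's rating is the primary one, Figure 1 bears on the primary outcome, and Figures 2 and 3 bear on secondary ratings only.

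**Working it through.** **1. Layout, counted from Figures 1 to 3.**

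| Form | VR items before the ratings | Of these, opinion items | Overall impression | Item just before pain | Pain, fear |
|---|---|---|---|---|---|
| Patient | 3, 4, 5, 8 (4 of 8) | 5, 8 | 7 | 8 | 9, 10 of 10 |
| Guardian | 5, 6, 7, 10 (4 of 10) | 7, 10 | 9 | 10 | 11, 12 of 12 |
| Provider | 2, 3, 8 (3 of 8) | 3, 8 | 7 | 8 | 9, 10 of 10 |

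On 3 of 3 forms the ratings are the last two items, every printed VR item precedes them, and the less-scary item sits directly before pain. The VR items that are not opinions are factual: prior use (patient 3, guardian 5) and use today (patient 4, guardian 6, provider 2).

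**2. Why the analysis cannot remove it.** Let the order shift the mean rating by o_VR in one arm and o_SC in the other. The estimated arm difference is then the true effect plus (o_VR − o_SC). Every participant gets the same order, so order is constant in the data and no GLM term can estimate the second part.

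**3. What a differential shift would do, as illustration only.** The documents give no size, so the shift b = o_VR − o_SC is assumed, in SD units. Inputs are 120 per arm (Section 3.0) and two-sided 0.05 (Section 4.0), with complete data and a normal approximation.

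SE = √(2/120) = 0.129. With no true effect, the rejection rate is Φ(b/SE − 1.96) + Φ(−b/SE − 1.96).

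For b = 0.10: b/SE = 0.775, so Φ(−1.185) + Φ(−2.735) = 0.118 + 0.003 = 12.1%.

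| Assumed b (SD) | Rejection rate with no true effect |
|---|---|
| 0 | 5.0% |
| 0.05 | 6.7% |
| 0.10 | 12.1% |
| 0.15 | 21.3% |
| 0.20 | 34.1% |

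For scale, the difference detectable with 80% power is (1.960 + 0.842) × 0.129 = 0.36 SD.

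**4. Whether a change part-way through could measure the effect.** Assume a switch at half enrolment, so 60 per arm on each version. The SE of the difference in treatment effect between versions is √(2/60 + 2/60) = 0.258, and the 95% half-width (t, 236 df) is 0.51 SD. For the treatment effect itself the half-width is 0.25 SD (t, 238 df). The comparison is therefore imprecise. It is also confounded with calendar time, since staff learning and case mix could change along with the form.

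**The case against.** The strongest case against is that no bias has been shown. The documents contain nothing that conflicts with the printed order, the size of any effect is unknown, and the table in step 3 rests on assumed shifts. That is correct. The point is about an avoidable risk and does not claim a known error.

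Several narrower objections also stand:

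- A reader might infer that the primary outcome is compromised on all three forms. Section 2.0 does not name the rater, so this cannot be said.
- A reader might call the less-scary item leading. Its wording names only a benefit, but its responses run evenly from strong disagreement to strong agreement.
- A reader might also object to the heading, "Use of Immersive Virtual Reality for Laceration Repairs in the Pediatric Emergency". Families have already been through consent, and children aged 8 to 17 through assent, and they know whether goggles were worn. The heading tells them little that is new, so changing it is not part of this point.
- Paper forms can be read ahead, so print order does not fully control what a rater has seen.
- Under the parent-first rule in Section 3.0, a helping parent has already answered the guardian form's VR questions. Reordering the child's form does not close that route.

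These objections limit what reordering can achieve. They do not supply a reason for asking the less-scary question first.

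**Conclusion.** The point holds as a design weakness that should be corrected. On all three forms the pain and fear ratings directly follow a judgement of VR's effect on fear, and the planned GLM could not separate a resulting arm difference from treatment. The concern is greatest for the patient form.

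The size and direction of any order effect are unknown. A reader might infer from the layout that results will be biased in favour of VR, or that the false-positive rate is raised by a stated amount. The documents support neither: the effect could run either way, and step 3 only shows what an assumed shift would do. A reader might equally infer that reordering would make these ratings free of bias. It would not, because raters would still know the arm.

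The case for change rests on three things: these items carry the primary outcome, the order effect may plausibly differ by arm, and removing it costs little. That the cost is low is a judgement based on short paper forms, and it assumes the change is made before first use. The documents do not say whether the forms are already in use.

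**What to change.** Before the first form is used:

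- Place the pain and fear ratings first on each form, ahead of the VR items and the overall-impression item. The patient form matters most.
- Keep the prior-use and used-today items for both arms. Limiting them to the VR arm would lose prior VR experience in controls, and with it the survey check on whether a control child received goggles.
- Add a "Did not use today" option to the VR opinion items that lack it: patient 5 and 8, guardian 10, provider 3 and 8. Guardian item 7 already has it.

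The cost is reprinting three forms with items reordered and one response option added. Sample size, significance level and visits do not change. Raters' knowledge of the arm remains, as does exposure through a helping parent who has completed the guardian form; both should be reported as limitations.

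If forms are already in use, there are two acceptable courses. One is to keep the order and report it as a limitation. The other is to change it and record the form version for each participant, stating that any difference between versions is confounded with calendar time and cannot be attributed to order.

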Patients will be separated into groups age 6-11 and 12-17. Patients will be randomized via a selection of a sealed envelope which will contain instructions for use of the VR goggles. The goggles utilized will be Lenovo Mirage Solo with DayDream, which are standalone VR headset with WorldSense Body Tracking. Research staff will coach the child on age-appropriate games, as previously determined by Lenovo.

The goggles will be cleansed with Oxivir Tb disinfectant wipes after each use and allowed to dry in room air prior to next use. Education will be provided to all ED providers on the proper cleansing protocol for the VR goggles (Figure 4). The disinfectant protocol will be available for all users during the study, and has been approved by the director of Infection Control at Children's Hospital of the King's Daughters.

Following the laceration repair, the patient, guardian and health care provider will be surveyed (Figure 1, 2, and 3) on paper surveys. The survey includes Likert-type scale questions, binary

questions as well as incorporates the Wong Baker Faces Pain Scale and Children's Fear Scale. The duration of the procedure will be recorded by the healthcare provider who completed the laceration repair. Time of procedure will be defined as from the time of irrigation to wound dressing. Patients and parents will both be filling out their own individual surveys. The parent should complete the survey first before the child should the child need assistance with completion. Patients and parents may decline to participate in any survey at any time.

The recruitment period will be from November 2021 until February 2021. Enrolled participants will not be compensated, and enrollment will be completely voluntary.

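### Patient survey item 9, which records the primary pain outcome, names no time period, so an unknown share of children could rate current pain instead of pain during the repair

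*Combined protocol and SAP*

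**What the plan says.** Section 2.0 (Objectives) asks whether VR goggles can "decrease patient pain and anxiety during simple laceration repairs", and states: "The primary outcome will be pain scores as assessed by the validated Wong Baker Faces Scale". Anxiety on the Children's Fear Scale is named alongside it. The section does not say whose rating is primary, but the patient form carries the child's own score.

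Section 3.0 (Project Procedures) sets the timing: "Following the laceration repair, the patient, guardian and health care provider will be surveyed". It gives no interval after the repair. The parent completes the survey before the child, in case the child needs help.

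On the patient form (Figure 1) the relevant items are:
- Item 6, symptoms: "6. During your stitches, did you have any of the following"
- Item 9, pain: "9. How would you rate your pain"
- Item 10, fear: "10. How would you rate how scared you were during the stitches"

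Items 6 and 10 name the period; item 9 does not. Guardian items 11-12 (Figure 2) and provider items 9-10 (Figure 3), which ask for pain and fear, have no time reference either. Section 4.0 (Statistical Analysis) plans a generalized linear model on the survey outcomes and Spearman correlations between the three raters. No visible text sets a recall period for any pain rating.

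**The concern.** A child who is handed the form after the repair can read item 9 in two ways: how much the repair hurt, or how much the wound hurts now. Only the first is the quantity in the objective. The form does not record which one the child had in mind, so no analysis under Section 4.0 can separate the two or correct for the mixture.

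At stake is the treatment comparison on a primary outcome. If VR acts on pain during the repair and current pain is the same in both arms, each child who rates current pain contributes no treatment difference, and the estimate shrinks towards zero. The planned correlations between raters are also exposed, because child, guardian and provider could each have a different period in mind.

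**Working it through.** **1. Wording.** Target period: during the repair (Section 2.0). Time of rating: after it (Section 3.0). Stem of item 9: no period. Stems of items 6 and 10: the stitches. The gap therefore shows within the form itself. It concerns the visible stem only; any wording printed with the faces scale cannot be checked.

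**2. Inputs for a size.** From the documents: 120 patients per group (Section 3.0) and two-sided alpha 0.05 (Section 4.0). No effect size, SD or power accompanies the 120, so there is no planned figure to reproduce. Assumed: an effect of d = 0.363 SD, chosen because a two-sample t test with 120 per arm then has 80.0% power; and a share f of children in each arm who rate current pain, with f varied.

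**3. Equal misreading, SD unchanged, current pain the same in both arms.** The effect becomes d × (1 − f):
- f = 5%: 0.363 × 0.95 = 0.345, power 75.8%
- f = 10%: 0.363 × 0.90 = 0.327, power 71.2%
- f = 20%: 0.363 × 0.80 = 0.290, power 61.0%

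**4. Same case at f = 20%, with the variance of the mixture.** Assume that misreaders score 0, that the procedural SD is 2.5 (variance 6.25) and that the control procedural mean m is 3, 4 or 5. The true effect is 0.363 × 2.5 = 0.9075 points, so the diluted difference is 0.8 × 0.9075 = 0.726. The variance in an arm with procedural mean μ is (1 − f) × 6.25 + f(1 − f)μ² = 5 + 0.16μ², with μ = m in the control arm and m − 0.9075 in the VR arm. The SD below is the square root of the average of the two variances.
- m = 3: variances 6.44 and 5.70, SD 2.46, d = 0.295, power 62%
- m = 4: variances 7.56 and 6.53, SD 2.65, d = 0.274, power 56%
- m = 5: variances 9.00 and 7.68, SD 2.89, d = 0.251, power 49%

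The single figure of 61% in step 3 thus becomes a range of 49-62%.

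**5. Unequal misreading with no true effect.** Let shares f1 and f2 rate current pain, and let every such child score c. The spurious difference is (f2 − f1)(m − c), and each arm's variance is (1 − f) × 6.25 + f(1 − f)(m − c)². For 10% against 20%:

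| Current pain c | Procedural mean m | Difference (points) | In SD | Rejection at nominal 5% |
|---|---|---|---|---|
| 0 | 3 | 0.30 | 0.118 | 14.9% |
| 0 | 4 | 0.40 | 0.148 | 20.7% |
| 0 | 5 | 0.50 | 0.172 | 26.4% |
| 2 | 3 | 0.10 | 0.043 | 6.3% |
| 2 | 4 | 0.20 | 0.083 | 9.8% |
| 2 | 5 | 0.30 | 0.118 | 14.9% |

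For 5% against 10%, rejection is 7.4-10.8% at c = 0 and 5.3-7.4% at c = 2. If c = m, the difference is zero and rejection is nominal. Swapping the arms reverses the sign.

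**The case against.** The strongest reply is that the context supplies the missing period. The form is about laceration repair, items 2, 4 to 8 and 10 all mention stitches, and item 9 sits between a statement about the stitches and a question about fear during them. A parent may also be there to help. This largely stands: most children will probably rate the repair. It reduces the ambiguity without removing it. The form states the period outright in items 6 and 10, parental help is conditional, and the parent's own pain item has no period either.

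Second, the artwork after item 9 is not shown and may carry an instruction. That stands as a limit on the point, which rests on the visible stem.

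Third, no size can be demonstrated. That is correct: every figure above depends on assumed inputs.

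A reader might infer something stronger, namely that the comparison is biased because children know their arm ("4. Did you use VR goggles for your stitches today") and because the item just before the pain rating ("8. The virtual reality goggles made the stitches seem less scary") has no meaning for control children. The documents do not support this. Knowing one's arm does not explain why a child would confuse now with then, and that preceding item names the stitches on the form given to both arms. Nothing indicates that misreading would differ by arm. The 15-26% rejection range also belongs to the extreme case in which every misreader has no current pain.

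**Conclusion.** The point holds as a correctable ambiguity in the instrument for a primary outcome. The visible stem of item 9 does not fix the period that the objective requires, and the data could not show afterwards who misread it.

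The main expected consequence is dilution, provided that current pain does not differ by arm. Under the stated assumptions, power falls from 80% to about 76%, 71% and 61% at 5%, 10% and 20% misreading, and the 20% figure lies between 49% and 62% once the mixture variance is counted. These are illustrations, not estimates for this trial.

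Bias from unequal misreading is a possibility only. For 10% against 20% with no true effect, rejection runs from nominal (current pain equal to procedural pain), through 6-15% (current pain 2), to 15-26% (current pain 0). It would also go too far to conclude that the pain score measures current pain or is unusable: the likely reading is the repair, and the share who depart from it is unknown.

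**What to change.** Before the forms are used, add *during the stitches* to the end of the stem of patient item 9, matching item 10. In the same revision, add *during the procedure* to guardian items 11-12 and provider items 9-10, so that all three raters, and the Spearman correlations between them, refer to one period. The adult forms should not be left out: if only the patient item is changed, the raters would be answering differently worded questions. Leave the scales themselves unchanged.

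The cost is one line on the patient form, two lines on each adult form, and a reprint of the paper surveys. No extra data, staff or participants are needed. If the forms are already in use, report the ambiguity as a limitation of the pain outcome and of the correlations between raters.
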